#### 4.3.2. Treatment Compliance With Baseline SSRI/SNRI Antidepressant

Compliance for each subject will be calculated based on the percent of the scheduled number of days that the baseline SSRI/SNRI antidepressant was actually taken within the double-blind phase. It is defined as:

%compliance = (number of days baseline SSRI/SNRI antidepressant taken / number of days in double-blind phase)\*100%.

The number of days in the double-blind phase will be calculated as the duration of double-blind treatment phase (i.e., completion or discontinuation date of the double-blind phase – date of first dose of study drug + 1).

Descriptive statistics on the percent compliance will be summarized by treatment group for the safety analysis set. In addition, percent compliance will be categorized as <60%, 60%-<80%, 80%-100%, >100% and the number and percentage of subjects in each category will be summarized.

#### 4.4. Extent of Exposure

Total duration of exposure (including days off drug) is defined as (date of last dose of study drug - date of first dose of study drug) + 1. Number of doses is defined as the total number of drug administrations. Taking more than 2 tablets within 4 hours is considered as overdose.

Descriptive statistics (N, mean, SD, median, minimum, and maximum) for total duration of exposure (including days off drug) and for number of doses will be presented by treatment group for the safety analysis set.

A by-subject listing of study drug administration will be provided.

#### 4.5. **Protocol Deviations**

In general, the following list of major protocol deviations may have the potential to impact subjects' rights, safety or well-being, or the integrity and/or result of the clinical trial. Subjects with major protocol deviations will be identified prior to database lock and the number and percentage of subjects with major protocol deviations will be summarized by category for the safety analysis set.

- Developed withdrawal criteria but not withdrawn
- Entered but did not satisfy criteria
- Received a disallowed concomitant treatment
- Received wrong treatment or incorrect dose
- Other

More categories may be included depending on the nature of the protocol deviation. A subject may be counted in more than one deviation category.

A by-subject listing showing the specific major protocol deviations will also be provided.

A summary of the number of subjects in the safety analysis set not meeting each inclusion/exclusion criterion will be presented.

#### 4.6. Prior and Concomitant Medications

Prior and concomitant medications will be coded using the World Health Organization Drug Dictionary (WHO-DD). Prior medications are defined as any therapy used before the day of first dose (partial or complete) of study drug. Concomitant medications are defined as any therapy

used on or after the same day as the first dose of study drug, including those that started before and continue after the first dose of study drug.

If the medication start date is recorded as partial or completely missing, then the medication will be considered to be concomitant unless it is known to be prior to the first administration of study drug based on partial start date or stop date or the CRF indicates that the medication was taken prior (prior medication flag=Yes) (see Section 2.10 for detailed classification of prior and concomitant medications).

Prior medications will be summarized by treatment group and base preferred term for the safety analysis set. The proportion of subjects who receive each prior medication will be summarized as well as the proportion of subjects who receive at least one prior medication. In addition, the number and percent of subjects who receive antidepressant medications prior to the study will be summarized.

Summaries of concomitant medications (other than antidepressant medications) will be presented by treatment group and base preferred term for the safety analysis set, for those medications used during the double-blind phase and for those used during the follow-up phase separately. Definitions for concomitant medications used during the double-blind phase and those used during the follow-up phase are provided in Section 2.10.2 and 2.10.3, respectively. The proportion of subjects who receive each concomitant medication will be summarized as well as the proportion of subjects who receive at least one concomitant medication.

In addition, summary tables of the antidepressant concomitant medications received during the study will be presented by treatment group, for those medications used during the double-blind phase and for those used during the follow-up phase separately.

A by-subject listing of all prior and concomitant medication will also be provided.

## 5. EFFICACY

All efficacy analyses will be based on the full analysis set.

The efficacy variables for this study are listed in Table 4.

Efficacy Variable		Endpoint
MADRS	• Change from baseline to the end of Week 6 in the MADRS total score	Primary
	• Correlation between baseline ISI score as a continuous variable and change from baseline to the end of Week 6 in the MADRS total score.	Secondary
	• Change from baseline to the end of Week 6 in the MADRS total score in subjects with baseline ISI score $\geq$ 15 versus subjects with baseline ISI score	Secondary

 Table 4: Efficacy Variables

Efficacy Variable		Endpoint
	<15.	
	
 
Proportion of responders on depressive symptoms scale (≥50% improvement in the MADRS total score from baseline to the end of Week 6)
 
	Secondary
	
 
Proportion of subjects with remission on depressive symptoms scale (MADRS total score ≤8, ≤10, ≤12 at the end of Week 6)
 
	Secondary
	• Change from baseline to the end of Week 6 in the MADRS total score in subjects with MDD with anxious distress versus subjects with MDD without anxious distress.	Secondary
	• Change from baseline to the end of Week 6 in the MADRS-6 total score	Secondary
ISI	• Shift in ISI score category from baseline to the end of Week 6.	Secondary
HAM-A	• Change from baseline to the end of Week 6 in the HAM-A total score	Secondary
	
 
Proportion of responders on anxiety symptoms scale (≥50% improvement in the HAM-A total score from baseline to the end of Week 6)
 
	Secondary
CGI-S	• Change from baseline to the end of Week 6	Secondary
SDS	• Change from baseline to the end of Week 6	Secondary
PHQ-9	• Change from baseline to the end of Week 6	Secondary
SHAPS	• Change from baseline to the end of Week 6	Secondary
PROMIS-SD	• Change from baseline to the end of Week 6	Secondary
PROMIS-Fatigue	• Change from baseline to the end of Week 6	Secondary
PGI-S	• Change from baseline to the end of Week 6	Secondary
EQ-5D-5L, VAS and health status index	• Change from baseline to the end of Week 6	Secondary
WLQ	• Change from baseline to the end of Week 6	Secondary

## 5.1. Analysis Specifications

## 5.1.1. Level of Significance

The primary efficacy endpoint will be evaluated at a 1-sided significance level of 0.05 using the MCP-Mod approach to test for dose-response. For all other analyses of the primary efficacy

endpoint and for all other efficacy endpoints, no multiplicity adjustment will be done will be presented.

For the interim analysis, a 1-sided 0.30 significance level will be used to test for dose-response using the MCP-Mod approach on the change in MADRS total score to the end of Week 6. No adjustment to the final significance level will be performed due to the interim analysis.

## 5.1.2. Data Handling Rules

As sensitivity analyses, the change in MADRS total score, MADRS-6 total score, HAM-A total score, and PHQ-9 total score will be analyzed using an analysis of covariance (ANCOVA) model, using last observation carried forward (LOCF) data. These analyses are further described in Sections 5.2.3.3, 5.3.4.2, and 5.3.8.2.

For the analyses of response of depressive symptoms based on MADRS total score (Section 5.3.1), remission of depressive symptoms based on MADRS total score (Section 5.3.2), response of anxiety symptoms based on HAM-A total score (Section 5.3.5), and response and remission of depressive symptoms based on PHQ-9 total score (Section 5.3.8.2), both observed case and imputed case where subjects with missing values will be imputed as non-responders/non-remitters will be presented.

For the graphical presentations of the cumulative response rates, defined as the percentage of subjects experiencing at least a given value of percent reduction from baseline to the end of Week 6 for MADRS total score (Section 5.3.1), HAM-A total score (Section 5.3.5), and PHQ-9 total score (Section 5.3.8.2), both observed and LOCF data will be presented. Since ISI is collected at only 1 postbaseline time point, the cumulative response curve for ISI (Section 5.3.3.2) will be presented using observed data.

## 5.1.3. Imputation Methods for Missing Items

For MADRS, imputation of the total score when there are missing items is described in Section 5.2.1. Likewise, for PROMIS-SD, PROMIS-Fatigue, WLQ and MADRS-6, imputation of the total score when there are missing items is described in Sections 5.3.10.1, 5.3.11.1, 5.3.14.1 and 5.3.15.1, respectively. For all other scales where multiple items are summed to create a total, if any item of the scale is missing at a visit, the total score for that scale at that visit will be left blank.

## 5.2. Primary Efficacy Endpoint

## 5.2.1. Definition

The primary efficacy endpoint is the change in MADRS total score from baseline to the end of Week 6. The MADRS will be performed by independent, centralized remote raters during the study. The MADRS is a clinician-administered scale designed to measure depression severity and consists of 10 items, each of which is scored from 0 (item not present or normal) to 6 (severe or continuous presence of the symptoms). The MADRS evaluates apparent sadness, reported sadness, inner tension, reduced sleep, reduced appetite, concentration difficulties, lassitude,

inability to feel, pessimistic thoughts, and suicidal thoughts. The recall period for the MADRS is 7 days.

A total score (0 to 60) is calculated by adding the scores of all 10 items. Higher scores represent a more severe condition. Imputation of the total score will be performed only when 1 item score is missing. If 2 or more items are missing, the total score will be left missing. The total score will be imputed by calculating the sum of the scores of the non-missing items and multiplying it by the ratio of the maximum possible number of items (i.e., 10) to the number of non-missing items (i.e., 9).

The MADRS change from baseline at Week 6 is calculated as (MADRS total score at Week 6 – Baseline MADRS total score). Negative changes in MADRS total score indicate improvement.

#### 5.2.2. Primary Estimand

The primary estimand, the main clinical quantity of interest to be estimated in the study, is defined by the following 4 components:

**Population:** subjects with MDD who have had an inadequate response to current antidepressant therapy with an SSRI/SNRI, as defined through appropriate inclusion/exclusion criteria to reflect the targeted patient population;

Variable: change in MADRS total score from baseline to the end of Week 6 (see Section 5.2.1);

**Intervention Effect:** the effect of the initially randomized treatment together with the oral SSRI/SNRI antidepressant that would have been observed had all subjects remained on their treatment throughout the double-blind phase;

Summary Measure: the difference in variable means.

The primary analysis will be based on the full analysis set and the MADRS total scores collected during the double-blind phase.

#### 5.2.3. Analysis Methods

Descriptive statistics of the actual values on Baseline, Day 8, Day 22, and Day 42 and the change from baseline to Day 8, 22, and 42 will be presented for MADRS total score by treatment group. A frequency distribution of the MADRS individual item scores at each time point will be provided by treatment group.

## 5.2.3.1. MCP-Mod Analysis

The primary efficacy endpoint will be evaluated using the generalized MCP-Mod approach. The MCP-Mod approach provides a method for dose-finding using model-based estimation rather than hypothesis testing via pairwise comparisons. The analysis will be done in two steps.

First, a mixed model for repeated measures (MMRM) analysis of the observed data from the placebo and JNJ-42847922 groups will be used as the method of addressing missing data and to

adjust for important covariates. The MMRM will include region (as defined in Section 2.6), time (scheduled Week), treatment (placebo and JNJ-42847922 dose groups), baseline insomnia status (present/absent), and treatment-by-time interaction as factors and baseline MADRS total score as a covariate. An unstructured variance-covariance matrix will be used for observations clustered by subject. In case of convergence problems, alternative variance-covariance structures will be tried in the following order, with the first structure that converges being used in the analysis: heterogeneous Toeplitz, standard Toeplitz, and AR(1) with separate subject random effect. Subjects in the full analysis set who do not have complete data will still contribute to the estimates at the end of Week 6, but will have less weight in the analysis than those subjects with complete data. The Kenward-Roger method will be used for approximating the denominator degrees of freedom. Based on the MMRM, the least-squares (LS) mean estimates for each JNJ-42847922 dose group and placebo at Week 6 and the corresponding variances will be obtained.

Subsequently, the generalized MCP-Mod approach will be applied towards the estimates obtained from the MMRM to analyze the dose-response relationship. This approach requires prespecification of a candidate model set. The actual candidate model set will depend on an interim analysis decision with two possible scenarios. The first scenario is when the 10 mg dose is not added after the interim analysis (i.e., subjects have been randomized to placebo, JNJ-42847922 20 mg and 40 mg dose groups only). For that scenario, using notation as in Bornkamp et al  $(2009)^1$ , the candidate set consists of the following 3 standardized model profiles (with the corresponding parameters): "linear" (no parameters), "emax" (ED50=1.053), and "exponential"  $(\delta = 18.20)$ . The second scenario is realized when the 10 mg dose is added after the interim analysis. For the second scenario, the candidate set is extended to the total of 4 standardized model profiles: "linear" (no parameters), "emax" (ED50=1.053), "exponential" ( $\delta$ =18.20), and "sigEmax" (ED50=14.14, h=8.496). Figure 2 below shows the extended set (of note, the maximum response is scaled to 1). Also, for the second scenario, the MCP-Mod model selection criteria will be based on the Akaike Information Criterion (AIC) with the k parameter equal to 0.5. As a sensitivity analysis, the maximum of the candidate model trend test statistics will be used as MCP-MOD model selection criterion.

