11.3. Efficacy Analyses

Primary estimand

The primary estimand, the main clinical quantity of interest to be estimated in the study, is defined by the following 3 components:

Population: subjects with MDD who have had an inadequate response to current antidepressant therapy with an SSRI/SNRI.

Endpoint: change in MADRS total score from baseline to the end of Week 6.

Measure of Intervention: the effect of the initially randomized treatment together with the oral SSRI/SNRI antidepressant that would have been observed had all subjects remained on their treatment throughout the double-blind phase.

The primary analysis will be based on the FAS and the MADRS total scores collected during the double-blind phase.

The primary efficacy endpoint will be evaluated at a 1-sided significance level of 0.05 using the MCP-Mod approach to test for dose-response. For all other analyses of the primary efficacy endpoint and for all other efficacy endpoints, no multiplicity adjustment will be done and nominal 1-sided p-values will be presented.

Primary efficacy endpoint

The primary efficacy endpoint is the change in MADRS total score from baseline to the end of Week 6. A mixed model for repeated measures (MMRM) analysis of the observed data from the placebo and JNJ-42847922 groups will be used as the method of addressing missing data. The MMRM will include region, time, treatment (placebo and JNJ-42847922 dose groups), baseline insomnia status (present/absent), and treatment-by-time interaction as factors and baseline MADRS total score as a covariate. An unstructured variance-covariance matrix will be used. Subjects in the FAS who do not have complete data will still contribute to the estimates at the end of Week 6, but will have less weight in the analysis than those subjects with complete data. The final analysis will use the generalized MCP-Mod approach⁴⁵ (a hybrid methodology that combines multiple comparison procedures with modeling techniques), which will be applied towards estimates obtained from the MMRM analysis to establish a dose-response signal and to

determine dose(s) to be used in the Phase 3 studies. MCP-Mod has been qualified by the European Medicines Agency. ¹⁰

In conjunction, the comparison between JNJ-42847922 and placebo will also be performed using the appropriate contrasts directly from the MMRM analysis using estimates at the end of Week 6.

Secondary efficacy endpoints

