#### 1.4. Sample Size Justification

The calculation of the sample size is based on the primary efficacy endpoint (change from baseline to the end of Week 6 for the MADRS total score). The assumptions for the effect size were based on published literature and the clinically meaningful difference between groups to be detected.

The total sample size is calculated on the basis of the generalized Multiple Comparison Procedure-Modeling (MCP-Mod) test applied to the placebo and the JNJ-42847922 dose groups at the final analysis. Approximately 280 randomized subjects will provide an average weighted power of approximately 85% depending on the underlying true dose-response shape, assuming a 1-sided significance level of 0.05, a treatment difference from placebo of 4.5 points in change in MADRS total score, a standard deviation of 10, and a 25% overall dropout rate.

The data cutoff for the interim analysis will be 6 weeks after randomization of 160 subjects, which corresponds to approximately 57% of the sample size of the study. This number of subjects provides approximately 93% power to detect a dose-response relationship, depending on

the underlying true dose-response shape, assuming a treatment difference of 4.5, and a standard deviation of 10 when tested by means of the MCP-Mod approach at the 30% significance level (1-sided).

Further details regarding the interim analysis will be specified in a separate charter and interim analysis SAP.

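### Optional improvement, not an error: a baseline-by-time term in the primary MMRM would guard against a small loss of Week 6 precision if the baseline slope differs by visit

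*SAP*

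**What the plan says.** SAP 5.2.3.1 gives the fixed effects of the primary MMRM as region, time, treatment, baseline insomnia status, "and treatment-by-time interaction as factors and baseline MADRS total score as a covariate". Protocol 11.3 gives the same model: "treatment-by-time interaction as factors and baseline MADRS total score as a covariate". Neither document has a baseline-by-time term or explains why a common slope was preferred.

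The model covers three post-baseline visits; SAP 5.2.3 says that "change from baseline to Day 8, 22, and 42 will be presented for MADRS total score by treatment group". On covariance, "An unstructured variance-covariance matrix will be used for observations clustered by subject". From this fit "the least-squares (LS) mean estimates for each JNJ-42847922 dose group and placebo at Week 6 and the corresponding variances will be obtained", and those estimates go into MCP-Mod. The pairwise comparisons in SAP 5.2.3.2 also use Week 6 contrasts from this model.

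The same model, with the baseline covariate swapped, is reused for HAM-A (5.3.4.2), SDS (5.3.7.2), PHQ-9 (5.3.8.2), SHAPS (5.3.9.2), PROMIS-SD (5.3.10.2), PROMIS-Fatigue (5.3.11.2) and MADRS-6 (5.3.15.2).

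**The concern.** The outcome is change from baseline, and its dependence on baseline need not be the same after one week as after six. The unstructured covariance lets variances and correlations differ by visit but leaves the mean slope common to all visits. If the slopes do differ, generalised least squares weights the common slope toward the visit with the smallest variance. The Week 6 means are then adjusted with a slope that suits Day 8 better than Day 42, and some variation explained by baseline stays in the Week 6 error. At stake is a little precision at the one visit that drives dose-response testing and dose selection.

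**Working it through.** **Inputs from the documents.** SAP 1.4: "assuming a 1-sided significance level of 0.05, a treatment difference from placebo of 4.5 points in change in MADRS total score", with "a standard deviation of 10, and a 25% overall dropout rate", and 280 randomized. SAP 1.5: initial allocation 2:1:1. SAP 5.2.3.1: linear, emax (ED50 1.053) and exponential (delta 18.20) candidates if 10 mg is not added.

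**Inputs assumed, because the documents do not give them.** Baseline MADRS SD 4 to 6. SD of change 6.5, 8.5 and 10 at Days 8, 22 and 42. Correlations between changes (Days 8-22, 8-42, 22-42) of 0.6, 0.4, 0.7 (set A) or 0.7, 0.6, 0.8 (set B). Visit slopes as listed below.

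**1. The plan's own figure.** SAP 1.4 states: "Approximately 280 randomized subjects will provide an average weighted power of approximately 85" per cent. Completers: 280 × 0.75 = 210, split 105 / 52.5 / 52.5. With an effect of 4.5 at 40 mg and the maximum-contrast test at 1-sided 0.05, power is 84.0% (linear), 92.5% (emax) and 81.7% (exponential). The average is (84.0 + 92.5 + 81.7)/3 = 86.1%, so the stated figure reproduces without crediting any variance reduction to baseline adjustment.

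**2. Where the common slope falls.** With residual covariance R, the common slope is b_c = (1′R⁻¹b)/(1′R⁻¹1), a weighted mean of the visit slopes b. For baseline SD 5, slopes −0.10/−0.25/−0.40 and set A, the weights on Days 8, 22 and 42 are 0.779, 0.052 and 0.169. So b_c ≈ −0.078 − 0.013 − 0.068 ≈ −0.158, against a true Day 42 slope of −0.40.

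**3. Inflation of the Week 6 variance.** Ratio = 1 + (b_42 − b_c)² × Var(baseline) / residual variance at Day 42.
- Same case: residual variance 100 − 0.40² × 25 = 96; ratio 1 + 0.2416² × 25/96 = 1.0152; SE up 0.76%; 280 × 0.0152 ≈ 4 subjects.
- Slopes −0.10/−0.30/−0.50, baseline SD 5, set B: b_c = −0.128; residual variance 93.75; ratio 1 + 0.372² × 25/93.75 = 1.0369; SE up 1.8%; 280 × 0.0369 ≈ 10 subjects.

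**4. Power.** For one dose against placebo, SE = 10 × √(1/105 + 1/52.5) = 1.690 and 4.5/1.690 = 2.662, so power is Φ(2.662 − 1.645) ≈ 84.5%. Removing an inflation of 1.0369 gives SE = 1.690/√1.0369 = 1.660 and power Φ(2.711 − 1.645) ≈ 85.7%, about 1.1 points more.

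| Slopes, Days 8/22/42 | Baseline SD, set | Variance ratio | SE increase | Subjects of 280 | Pairwise power lost (points) |
|---|---|---|---|---|---|
| Equal | any | 1.000 | 0 | 0 | 0 |
| −0.10/−0.20/−0.30 | 4, A | 1.004 | 0.2% | 1 | 0.1 |
| −0.10/−0.20/−0.30 | 6, B | 1.013 | 0.65% | 4 | 0.4 |
| −0.10/−0.25/−0.40 | 5, A | 1.015 | 0.76% | 4 | 0.5 |
| −0.10/−0.30/−0.50 | 5, B | 1.037 | 1.8% | 10 | 1.1 |
| −0.10/−0.30/−0.50 | 6, B | 1.054 | 2.65% | 15 | 1.6 |
| 0/−0.30/−0.60 (extreme) | 6, A to B | 1.093 to 1.131 | 4.5 to 6.3% | 26 to 37 | 2.7 to 3.7 |

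For ratios 1.0152 to 1.0369, average MCP-Mod power rises from 85.9% (step 1 recomputed in a separate Monte Carlo run) to 86.3-87.0% with the interaction.

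**5. Simulation check.** Each scenario had 1,500 trials of 280 subjects, with about 25% missing at Week 6 completely at random, and both models were fitted. The mean SE of the Week 6 contrast, common slope over by-visit slope, was 1.000 (equal slopes), 1.008 (−0.10/−0.25/−0.40), 1.015 (−0.10/−0.30/−0.50) and 1.051 (extreme). Bias was at most 0.024 points in either model.

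**The case against.** The case for leaving the model alone is reasonable. The common slope is prespecified, and protocol and SAP agree on it. Region and insomnia status also enter without time interactions, so the model is consistently parsimonious. Protocol 11.8 says the trial is not confirmatory. The choice of dose-response shape moves recomputed power from 81.7% to 92.5%, far more than this term does. The LOCF ANCOVA in SAP 5.2.3.3 already fits a baseline slope at the endpoint alone.

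What stands is that the effect is small and that its premise, slopes that differ by visit, is not in the documents. The LOCF ANCOVA answers only in part, because it is a sensitivity analysis that handles missing data differently. None of these arguments identifies a cost of adding the term, and with equal slopes the standard error did not change.

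A reader might also infer that, with 25% dropout, the Week 6 means are biased because they borrow from earlier visits through a wrong mean model. The documents do not support that. No bias was seen under random missingness, and response-driven dropout gave at most about 0.06 points in both models. A shift of 0.3 to 0.6 points in favour of drug appeared only in a deliberately adverse case, in which higher baseline severity raised dropout on placebo and lowered it on active drug. Nothing in the plan predicts such a pattern.

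**Conclusion.** The point holds as a free improvement, not as an error. Any loss is conditional on visit-specific slopes. For plausible values it is about 0-2% in SE and about 0-1 point of power. The corner with baseline SD 6, the steepest plausible slopes and the higher correlations reaches 2.65% and 1.6 points, and only the extreme scenario goes further. These sizes rest on the assumed baseline SD, change SDs, correlations and slopes.

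Two stronger readings should be resisted. The documents do not show that precision is lost, since they give no slopes. They also do not show the trial to be underpowered, since the figure of about 85% reproduces without this term.

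**What to change.** Add a baseline MADRS total score-by-time interaction to the MMRM in SAP 5.2.3.1 before unblinding, and either align protocol 11.3 or record the difference in the SAP. For consistency, add the matching baseline-by-time term to the secondary MMRMs that cite 5.2.3.1; the gain on those scales was not computed. The cost is 2 parameters per model (three visit slopes in place of one), using data already collected. If the sponsor prefers the common slope, one sentence giving the reason would be enough.
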